The study population consists of patients who underwent curative surgical resection for HCC. Multiple datasets will be established in the prospective study for model optimization and validation, and all datasets will be constructed in accordance with strict inclusion and exclusion criteria.

(1) Patient Inclusion and Exclusion Criteria

Inclusion Criteria

Histopathologically confirmed diagnosis of hepatocellular carcinoma;

Aged between 18 and 75 years old;

Underwent curative resection (R0 resection) for primary hepatocellular carcinoma;

Complete postoperative formalin-fixed paraffin-embedded (FFPE) H&E-stained tissue slides eligible for digital scanning;

Complete and accessible preoperative CT/MRI images, clinicopathological data and follow-up data, including but not limited to age, gender, HBsAg status, liver cirrhosis background, AFP and PIVKA-II levels, tumor size and number, CNLC stage, AJCC 8th TNM stage, BCLC stage, vascular invasion status, tumor differentiation grade, detailed postoperative adjuvant therapy regimens and medication records, as well as postoperative tumor recurrence and survival data;

Signed the informed consent form for the prospective study.

Exclusion Criteria

Received anti-tumor treatments such as TACE, targeted therapy, immunotherapy and radiotherapy at non-collaborative medical centers before surgery, with unavailable original imaging and clinical baseline data;

Combined with primary malignant tumors of other organs;

Positive surgical margins after surgery (R1 or R2 resection);

Poor quality of pathological tissue slides (such as severe fading, folding, breakage or insufficient

tissue volume), which cannot be used for digital scanning or reliable analysis;

Severe missing of clinical or follow-up data.

(2) Definition and Source of Datasets

A multi-center and multi-stage data collection strategy will be adopted for all datasets, which are strictly divided according to purposes to ensure mutual independence of the training set, validation set and test set and avoid data leakage.

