A multi-center collaboration model will be adopted for the prospective cohort. ① Prospective Observational Cohort: A total of 1,000 patients will be consecutively enrolled from 10 to 15 medical centers. Pathological slides will be collected for digital scanning, and preoperative imaging data will be imported into the model. No clinical intervention will be conducted; only model predictions and actual clinical outcomes will be recorded to evaluate the model's performance in real clinical settings. ② Prospective Interventional Cohort: A randomized controlled trial will be carried out in 3 to 5 medical centers with a planned enrollment of 600 patients. After obtaining patients' informed consent, patients will be randomly assigned to the intervention group (AI model-assisted decision-making) and the control group (standard clinical decision-making). Physicians in the intervention group will formulate treatment plans with reference to the optimal treatment regimens predicted by the AI model; the control group will receive routine treatment. Clinical outcomes will be compared between the two groups to provide high-level evidence for the clinical utility of the model.

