3.4.2 Sample Size for Prospective Study Phase

(1) Sample Size for Prospective Observational Validation ($n = 1,000$)

Estimation Basis: This phase evaluates the correlation strength between model predictions and real clinical prognosis (C-index) using sample size formulas for survival analysis. Relapse-Free Survival (RFS) is taken as the primary endpoint.

Assuming the 12-month RFS rate of the control group is 60% and the corresponding HR of the model-consistent group is 0.7, a total of 256 events are expected. Simulated by PASS 2021 software, more than 300 events can be observed in 1,000 cases within a 24-month study period (12 months for enrollment + 12 months for follow-up), which meets the requirements of statistical power and supports stratified analysis.

(2) Sample Size for Prospective Interventional Study

Estimation Basis: This phase is a Randomized Controlled Trial (RCT) with strictly calculated sample size, taking RFS as the primary endpoint.

Sample size formula for Log-Rank test is adopted with the following parameter settings: Baseline event rate: The 12-month RFS rate of the standard treatment group (Arm B) is 65%. Effect size: The 12-month RFS rate of the AI-assisted decision-making group (Arm A) is increased by an absolute value of 10% (up to 75%), corresponding to $HR = 0.67$. Significance level (α): 0.05. Statistical power ($1-\beta$): 80% (conventional standard for RCT). Accrual time: 18 months. Follow-up time: 12 months. Dropout rate: 10%.

Calculated by PASS 2021 software, a total of 200 events are required. Considering the dropout rate, the total required sample size is 600 cases (300 cases in each group). This sample size can detect the clinical difference corresponding to $HR = 0.67$ and meet the power requirements under follow-up and dropout conditions.

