Random (MCAR); multiple imputation is used for data Missing at Random (MAR); selection models are applied for data Missing Not at Random (MNAR). Sensitivity analysis is conducted to compare results obtained by different missing data processing methods.

Definition of statistical analysis datasets:

Full Analysis Set (FAS): Includes all randomized patients who received at least one efficacy assessment, analyzed according to the Intention-To-Treat (ITT) principle.

Per-Protocol Set (PPS): Includes patients who fully complied with the research protocol, excluding patients with major protocol violations.

Safety Set (SS): Includes all patients who received at least one treatment, used for safety evaluation.

Primary analysis is based on the FAS, and the PPS is used for sensitivity analysis to verify the robustness of results.

Statistical methods for primary outcome indicators: For categorical variables (such as treatment response grouping), weighted F1-score and macro-average AUC are taken as main evaluation indicators, and Cohen's Kappa coefficient is used to assess the consistency between model predictions and actual clinical conditions. For survival data (RFS and OS), the Kaplan-Meier method is used to draw survival curves, the Log-rank test is used for inter-group comparison, and the Cox proportional hazards regression model is established to calculate the Hazard Ratio (HR) and its 95% confidence interval while adjusting for potential confounding factors such as age, gender and TNM stage.

Statistical methods for secondary outcome indicators: Decision Curve Analysis (DCA) is used to evaluate the clinical net benefit of the model. Calibration Curve and Brier Score are used to assess the accuracy of predicted probabilities. Repeated-measures Analysis of Variance is used for inter-group comparison of continuous variables. The Mann-Whitney U test is adopted for ordinal variables such as physician adherence and decision confidence scale scores.

Algorithm stability evaluation: Bootstrap sampling (1,000 repetitions) is used to calculate the 95% confidence interval of model performance indicators for stability assessment. SHapley Additive exPlanations (SHAP) values are used to analyze feature importance and improve model interpretability. Intraclass Correlation Coefficient (ICC) is calculated to evaluate the consistency of the model across different centers; $ICC > 0.75$ is regarded as good consistency.

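### Part Two makes eligibility depend on follow-up that does not exist at enrolment, and the primary set called ITT omits randomised patients without an efficacy assessment

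*Protocol*

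**What the plan says.** **Eligibility, Protocol section 3.1, Part Two.** The inclusion list asks for "Complete and accessible preoperative CT/MRI images, clinicopathological data and follow-up data". The items named under that heading end with "detailed postoperative adjuvant therapy regimens and medication records, as well as postoperative tumor recurrence and survival data". The exclusion list adds "Severe missing of clinical or follow-up data", without defining how much missing data is severe.

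**Scope.** The list is introduced with "Multiple datasets will be established in the prospective study for model optimization and validation", and all of these datasets are to follow the criteria. The datasets then listed are the observational cohort ("A total of 1,000 patients will be consecutively enrolled from 10 to 15 medical centers") and the trial ("A randomized controlled trial will be carried out in 3 to 5 medical centers with a planned enrollment of 600 patients").

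**Endpoint, section 3.3.** RFS runs from randomisation to recurrence or death from any cause.

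**Analysis sets, section 3.8.** The Full Analysis Set is defined thus: "Includes all randomized patients who received at least one efficacy assessment, analyzed according to the Intention-To-Treat (ITT) principle". It is the primary set. The only other efficacy set is the Per-Protocol Set, used for sensitivity analysis.

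**Expected loss.** Section 3.4.2 allows 10% dropout in the trial, and section 3.8 plans imputation, selection models and sensitivity analyses for missing data.

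**The concern.** There are two separate faults, and they act at different points.

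The first is eligibility. The wording nearly repeats the retrospective list in Part One, where follow-up is already on file. In a prospective study it makes entry depend on the future. A site applying it can settle a patient's eligibility only once it is known whether follow-up was complete. In the observational cohort the patients are then no longer consecutive. In the trial it gives a written ground for calling a patient ineligible after allocation.

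The second is the analysis set. A set that requires a post-randomisation assessment is not the set of all randomised patients, whatever its label. Death is part of RFS, so a patient can have a primary event without ever being assessed. The Per-Protocol Set is narrower still, so no planned efficacy analysis would show the effect of the omission.

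At stake is the comparability of the randomised arms. Physicians in the AI arm act on the model's output and so know the arm, which makes exclusions that differ by arm possible.

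**Working it through.** **Step 1: timing of the required data.**
- Preoperative imaging, slides and baseline clinicopathology exist at enrolment.
- Adjuvant regimen and medication records: in the trial, the treatment plan is made after allocation (section 3.1), so complete records come later.
- Recurrence and survival data: the RFS clock starts at randomisation (section 3.3), so they cannot exist then.

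**Step 2: the rule against the rest of the protocol.**
- Consecutive enrolment of 1,000 patients (section 3.1) cannot hold if inclusion waits on later follow-up.
- A 10% dropout allowance (section 3.4.2) presumes that patients with incomplete follow-up were validly enrolled.
- The missing-data methods (section 3.8) presume that such patients are kept.

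**Step 3: what the Full Analysis Set rule changes.** A patient censored at time zero enters no risk set, so censoring at randomisation and exclusion give the same Kaplan-Meier, log-rank and Cox results. A detected recurrence implies an assessment. The rule therefore alters the estimate mainly through deaths known to have occurred before any assessment.

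**Step 4: the plan's own figure.** Inputs from section 3.4.2: 12-month RFS 65% against 75%, HR 0.67, alpha 0.05 (two-sided by section 3.8), power 80%, 300 per arm.
- HR: ln(0.75)/ln(0.65) = 0.668.
- Schoenfeld: 4 × (1.960 + 0.842)² / (ln 0.67)² = 4 × 7.849 / 0.1604, which rounds up to 196 events.
- Freedman: (1.67/0.33)² × 7.849 = 25.61 × 7.849, just over 201, rounded up to 202.
- Power at 200 events is 80.8%.

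The stated 200 events reproduce.

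**Step 5: possible size.** The documents give no exclusion pattern, so these patterns are assumed. The simulation used 300 per arm, exponential RFS with 65% control RFS at 12 months, uniform accrual over 18 months plus 12 months of follow-up, 10% per year random loss, a Cox model, and 1,500 runs per scenario. Early events are those in the first 3 months: 1 − 0.65^(3/12) = 10.2% of controls, or about 31 of 300. Under the null the AI arm has the same rate, so 30% of its early events is about 9 patients and 50% about 15.

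| Patients removed | Number removed (null) | Mean HR, true 1.00 | Type I error | Mean HR, true 0.67 |
|---|---|---|---|---|
| None | 0 | 1.00 | 5.1% | 0.67 |
| Lost at random before 12 months, event-free | about 50 | 1.00 | 4.9% | 0.67 |
| Lost at random before 3 months, event-free | about 15 | 1.01 | 5.4% | 0.67 |
| 30% of early events, both arms | about 18 | 1.00 | 4.8% | 0.67 |
| 30% of early events, AI arm only | about 9 | 0.94 | 8.1% | 0.63 |
| 50% of early events, AI arm only | about 15 | 0.90 | 13.7% | 0.60 |

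The simulation error of a 5% rate is √(0.05 × 0.95 / 1500) = 0.6 percentage points, so the first four rows do not differ from nominal. These runs concern the comparison between arms only. They do not assess absolute RFS or model calibration in the observational cohort.

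**The case against.** The strongest reply is that the two rules do not connect. Membership of the Full Analysis Set depends on randomisation and one assessment, not on the eligibility list. No sentence removes a randomised patient from it for later failing that list. The set that drops protocol violators is the Per-Protocol Set, which is only a sensitivity analysis. This stands. A reader might infer that the eligibility wording by itself breaks the ITT analysis; the documents do not say so. The wording permits post-allocation exclusions but does not order them.

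A reader might also take the 10% dropout, 0.10 × 600 = 60 patients, as the number that would disappear from the primary analysis. That is not supported either. The allowance covers the whole study, and a patient who drops out after one assessment stays in the set. Nor do the documents give any split of excluded events between arms, so an example with a chosen lopsided split shows only what was assumed.

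It can further be said that the eligibility phrase is carried-over text meaning willingness to be followed, and that the blinded adjudication committee (section 3.5) might count an early death as an assessment. Both are possible, but neither is written. An eligibility rule that cannot be applied at consent, and a set that leaves early deaths undecided, still need correction.

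**Conclusion.** Wrong as written, on both counts. Part Two eligibility depends on data that arise after enrolment and contradicts the protocol's own consecutive enrolment, dropout allowance and missing-data plan. The primary set is called ITT but is not all randomised patients; read literally, it omits deaths before the first assessment, and no wider efficacy set is defined. The ITT point concerns the trial only; in the observational cohort the fault is selection on outcome availability.

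The size of the bias cannot be derived from the documents. For the comparison between arms it is essentially nil if exclusions are random or balanced. It is real only if they are linked to outcome and differ by arm: in the assumed AI-arm-only scenarios, a null HR of about 0.94 to 0.90 and a type I error of about 8% to 14%. For the analysis-set rule alone, those 9 to 15 patients would nearly all have to be deaths before any assessment, and the documents give no rate for these.

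**What to change.** 1. In section 3.1, Part Two, limit eligibility to what is available at enrolment: preoperative imaging, scannable slides, baseline clinicopathology and consent. Delete follow-up data, postoperative regimens and medication records, and recurrence and survival data from the inclusion criterion. Delete the reference to follow-up from the missing-data exclusion.
2. In section 3.8, define the primary set as all randomised patients by assigned arm. Count deaths before any assessment as RFS events, and censor the other patients without an assessment at last known status.

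The cost is protocol wording. The 200 events and 600 patients stay as stated. The change should be made before enrolment, because patients screened out or not followed cannot be recovered afterwards.

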3.2 Deployment and Intervention of AI System

Aiming to solve the clinical problems of high heterogeneity in postoperative treatment response and difficulties in efficacy prediction for hepatocellular carcinoma, this study intends to construct the Hepatocellular Mixture-of-Experts (HepMoE) multimodal intelligent decision-making system. By fusing multimodal data including pathological imaging and clinical data, this system realizes individualized efficacy prediction and intelligent support for precise treatment decision-making. Centered on digital whole-slide pathology images (multiple stains of H&E and IHC: CK7, CK19, Ki-67), combined with structured clinical information (such as TNM stage, Child-Pugh classification and AFP level), this system innovatively incorporates medical imaging data (contrast-enhanced CT/MRI). Relying on the Mixture-of-Experts framework driven by pathological large models, a multimodal deep learning model is constructed to provide an intelligent solution for postoperative adjuvant therapy of hepatocellular carcinoma.

Equipped with the latest multimodal model capabilities, the HepMoE system fully leverages the achievements of self-supervised representation learning on large-scale whole-slide image corpora. Through transfer learning and fine-tuning mechanisms, HepMoE can efficiently extract cellular and histological phenotypic features from H&E and IHC stained images, and capture tumor morphology, tumor immune microenvironment and molecular phenotypic heterogeneity.

The model adopts Stain-specific Expert Networks to decouple features and conduct fine-grained modeling for different staining channels (H&E, CK7, CK19, Ki-67). A Gated Fusion Module dynamically integrates multimodal inputs to balance the contribution of morphological and immune features. CT/MRI images will be standardized (e.g., pixel normalization), tumor lesions will be automatically segmented using 3D U-Net or ViT models, and radiomic features (such as texture, shape and intensity features) and deep learning features will be extracted. On the basis of clinical variables (such as TNM stage, Child-Pugh classification and AFP level) and textual

pathological reports, individualized treatment benefit assessment and prediction of adjuvant therapy response are realized. Finally, HepMoE will form an integrated precise treatment auxiliary system combining pathological large model representation, interpretable decision-making of imaging models and clinical integration, providing a promotable intelligent decision-making platform for postoperative adjuvant therapy of hepatocellular carcinoma.

3.3 Evaluation Index System (Algorithm Performance, Clinical Utility, System Stability)

This study comprehensively evaluates the overall value of the AI model from three dimensions: algorithm performance, clinical utility and system stability.

Evaluation of Algorithm Performance

Conducted mainly during model development and validation, quantitative indicators are used to objectively assess the accuracy and robustness of the tumor immune microenvironment identification model and treatment response prediction model.

For the tumor immune microenvironment identification model: At the pixel level, Dice Similarity Coefficient (DSC) is used to evaluate the coincidence degree between segmentation results and expert annotations, and Intersection over Union (IoU) is adopted as a supplementary indicator. At the regional level, Precision, Recall and F1-Score are used to evaluate the recognition performance of specific components in the immune microenvironment.

For the treatment response prediction model: Area Under the Receiver Operating Characteristic Curve (AUC-ROC) is used to evaluate the binary classification ability of the model, and macro-average and micro-average AUC values are calculated. Accuracy, Precision, Recall and F1-Score calculated based on the confusion matrix are used to evaluate the performance of multi-classification tasks. Calibration Curve and Brier Score are used to assess the accuracy of predicted probabilities.

Evaluation of Clinical Utility

Conducted in the prospective study phase, focusing on evaluating the actual impact of the model on clinical decision-making and patient prognosis.

Primary clinical endpoints: Relapse-Free Survival (RFS), defined as the time from randomization to tumor recurrence or death from any cause. The Kaplan-Meier method is used for survival analysis, the Log-rank test is adopted for inter-group comparison, and the Hazard Ratio (HR) and its 95% confidence interval are calculated. Overall Survival (OS), defined as the time from randomization to death from any cause, is analyzed using the same statistical methods.

Secondary clinical endpoints: Treatment decision change rate, calculated as the proportion of cases where AI recommendations are inconsistent with physicians' initial treatment plans. Physician adherence, defined as the proportion of physicians in the intervention group who finally follow AI recommendations. Decision Curve Analysis (DCA) is used to evaluate the clinical net benefit of the model, and standardized net benefit values under different threshold probabilities are calculated. A 1–5 point Likert scale is used to assess changes in physicians' decision confidence.

Evaluation of System Stability

Focusing on the operational performance and reliability of the AI system in real clinical settings.

Technical performance indicators: Inference speed, recording the average time and standard deviation for processing a single whole-slide image. System availability rate, calculated as: $\text{Availability Rate} = (1 - \text{Downtime} / \text{Total Operating Time}) \times 100\%$. Concurrent processing capability, testing the system performance when processing multiple requests simultaneously. API response time, monitoring the communication delay of the interface connected to the hospital

information system.

Usability evaluation: The System Usability Scale (SUS) is adopted, which contains 10 items with a 5-point Likert scale. The total score is converted into a percentage for evaluation. Task completion rate test is conducted to record the success rate of users completing specific operations within the specified time.

Reliability evaluation: Long-term monitoring of relevant indicators including Mean Time Between Failures (MTBF) (the average time for continuous normal operation of the system) and Mean Time To Repair (MTTR) (the average time for system recovery after failure). Error rate statistics are performed to classify and record various system errors and their occurrence frequencies.

All evaluation results will be summarized into a comprehensive evaluation report to support model optimization and clinical application. Data collected during the evaluation will be stored in a dedicated database to facilitate subsequent in-depth analysis. A systematic evaluation system ensures that the artificial intelligence model meets clinical application standards in terms of accuracy, practicality and reliability.

3.4 Sample Size Calculation (Description of Parameter Sources and Calculation Tools for Sample Size)

This study includes multiple phases of retrospective model development and prospective clinical validation with different research objectives, so the basis and methods for sample size estimation vary in each phase. This section elaborates the basis, parameter sources and methods for sample size calculation of each phase, and clearly presents key calculation formulas.

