(2) Construction and Multi-level Clinical Validation of Treatment Response Prediction Model

This is the core part of the study. Based on the quantified tumor immune microenvironment features output by the above model, combined with imaging data and essential clinical variables (such as TNM stage, Child-Pugh liver function classification and AFP level), a classification model will be built to predict patients' responses to four types of postoperative adjuvant therapy regimens: surgery alone, surgery combined with TACE, surgery combined with TACE plus systemic therapy, and surgery combined with systemic therapy alone. A strict hierarchical validation strategy will be adopted in this part.

Model Training Phase

Retrospective data from our center (n=1500) will be used. Inclusion criteria for patients in this phase: ① Histopathologically confirmed HCC; ② Underwent curative surgical resection; ③ Complete preoperative contrast-enhanced CT/MRI images, records of postoperative adjuvant therapy and follow-up data are available. Definition of treatment response: The primary endpoint is Relapse-Free Survival (RFS), and secondary endpoints include Overall Survival (OS) and Objective Response Rate (ORR). Multi-category machine learning algorithms (such as Gradient Boosting Decision Tree and Deep Neural Network) will be used for model training to output the most beneficial treatment regimen for each patient.

Internal Validation Phase

An independent validation set (n≈500, no overlap with the training set) will be randomly divided from the data of our center for preliminary evaluation of the model's discriminative performance and hyperparameter tuning to prevent overfitting.

External Validation Phase 1 (Retrospective Validation and Model Calibration)

Retrospective data (n=3000) will be collected from 8 to 10 medical centers nationwide. The main purposes of this phase are: ① To validate the model performance on larger and more heterogeneous external datasets; ② To calibrate or slightly optimize the model according to

validation results and finalize the predictive model.

External Validation Phase 2 (Large-scale Retrospective Validation)

The finalized model will be tested on a brand-new large-scale retrospective dataset (n=10,000) from 3 to 5 medical centers to further enhance the level of evidence and provide a solid basis for prospective studies.

(3) Study Population

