A total of 1,500 eligible surgical patients from our center will be enrolled and randomly divided into the model training set (n=1000) and internal validation set (n=500) at a ratio of 2:1, for model training, preliminary validation and optimization respectively. A total of 400 eligible patients have been enrolled so far, and the remaining 1,100 patients will be continuously recruited from the historical medical records of our center according to the inclusion and exclusion criteria.

A multi-center collaboration model will be adopted for external validation. ① External Validation

Set 1: A total of 3,000 retrospective cases from 8 to 10 domestic medical centers will be included for multi-center retrospective validation and model calibration, so as to verify the model's generalization ability across different institutions and conduct calibration or limited iterative optimization on the initial model. ② External Validation Set 2: A total of 10,000 retrospective cases from 3 to 5 large domestic medical centers will be included for the final test of the finalized model to fully evaluate its effectiveness and stability. Only forward validation will be performed on this dataset using the locked model without any parameter adjustment.

Part Two: Clinical Validation of Hepatocellular Carcinoma Adjuvant Therapy Prediction Model - Prospective Study

(1) Prospective Observational Study

A total of 1,000 eligible postoperative HCC patients will be consecutively enrolled from 10 to 15 medical centers. Preoperative imaging data, postoperative WSIs and clinical data will be collected and imported into the model to obtain predicted treatment regimens. No intervention will be implemented on actual clinical decisions in this phase. Researchers will record model prediction results and actual clinical decisions. Patients will be divided into the prediction-consistent cohort and prediction-inconsistent cohort according to whether the actual clinical decisions are consistent with model predictions. Long-term follow-up will be conducted to observe patients' actual prognosis, so as to evaluate the consistency between model predictions and actual outcomes, as well as the model's performance degradation in real-world settings.

(2) Study Population

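### RFS and OS are defined only from randomisation, but RFS is also the primary endpoint of an observational cohort that is never randomised, and that cohort's consistency grouping has no date

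*Protocol*

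**What the plan says.** Section 3.3, under clinical utility, sets the scope as the whole prospective phase: "Conducted in the prospective study phase, focusing on evaluating the actual impact of the model on clinical decision-making and patient prognosis". The endpoint follows: "Primary clinical endpoints: Relapse-Free Survival (RFS), defined as the time from randomization to tumor recurrence or death from any cause". OS has the same origin. The protocol gives no other RFS or OS time origin.

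The prospective phase has two cohorts. The interventional one (600 patients) is randomised. The observational one (1,000 consecutive patients) is not: "No intervention will be implemented on actual clinical decisions in this phase". Section 3.1, Part Two, groups the observational patients as follows: "Patients will be divided into the prediction-consistent cohort and prediction-inconsistent cohort according to whether the actual clinical decisions are consistent with model predictions". It does not say on what date the decision counts as made.

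Section 3.4.2 (1), on the observational cohort, states: "Relapse-Free Survival (RFS) is taken as the primary endpoint". It assumes that "the 12-month RFS rate of the control group is 60" per cent, that the model-consistent group has HR 0.7, and that 256 events are expected.

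**The concern.** A time-to-event endpoint needs a time zero that every patient in the analysis has. The observational patients have no randomisation date, so someone must later choose another origin, possibly with the data in view. Both the HR between the two groups and the C-index named in section 3.4.2 depend on that choice.

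The choice matters because of the grouping. Consistency cannot be known at surgery: the model needs postoperative slides, and there must be an adjuvant decision to compare with its output. If the clock starts before that decision, or if patients are sorted by the treatment they went on to receive, early relapses are assigned to a group because of the outcome. The prospective inclusion criteria make sorting by delivered treatment a practical risk, since they call for "detailed postoperative adjuvant therapy regimens and medication records, as well as postoperative tumor recurrence and survival data". Section 3.3 also distinguishes a physician's initial plan from what is finally followed, so the decision can change over time.

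**Working it through.** **1. The plan's own figure.** Inputs from sections 3.4.2 and 3.8: HR 0.7, two-sided alpha 0.05. Power of 80% is stated for the RCT only and is assumed here.

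- Freedman: (1.960 + 0.842)² × ((1 + 0.7)/(1 − 0.7))² = 7.849 × 32.11 = 252.04, rounded up to 253. The stated 256 is reproduced to within about 1%.
- Schoenfeld, equal groups: 4 × 7.849/(ln 0.7)² = 246.8, rounded up to 247. Power at 256 events is 81%.
- Events available: control hazard λ = −ln 0.6 = 0.511 per year, follow-up uniform over 12 to 24 months. Event probability is 1 − (e^−λ − e^−2λ)/λ = 0.530 for controls and 0.412 at HR 0.7. With 500 per group and no dropout, 500 × (0.530 + 0.412) = 471, which agrees with the plan's statement of more than 300.

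The event count is not at fault. It confirms that the cohort was sized on a two-group RFS comparison, which needs a time zero.

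**2. The passages together.** Section 3.3 starts the clock at randomisation for the whole prospective phase. Section 3.1 gives the observational cohort no randomisation. Section 3.4.2 makes RFS its primary endpoint. These three cannot all be applied. Section 3.8 does not resolve it: its full analysis set is also defined on randomised patients.

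**3. What an unsuitable origin could do.** This is a simulation with no true effect, 1,000,000 patients per setting, hazard 0.511 per year and censoring uniform over 12 to 24 months. The clock starts at surgery, and a patient who relapses before planned adjuvant therapy is counted as surgery alone. The protocol gives none of the following, so they are assumptions: delay to adjuvant start of 1 to 3 months, 30 to 70% planned for adjuvant therapy, and a plan independent of the recommendation. The share recommended adjuvant therapy is varied over its full range because the model chooses among "surgery alone, surgery combined with TACE, surgery combined with TACE plus systemic therapy, and surgery combined with systemic therapy alone".

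| Share recommended adjuvant therapy | HR, consistent vs inconsistent, no true effect |
|---|---|
| 100% | 0.53 to 0.89 |
| 75% | 0.74 to 0.95 |
| 50% | about 1.00 |
| 25% | 1.05 to 1.36 |
| 0% | 1.11 to 1.89 |

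The sign changes because an early relapse makes a patient inconsistent if adjuvant therapy was recommended, but consistent if surgery alone was. The value near 1.00 at 50% is a cancellation: with a 2-month delay and 50% planned, it combines about 0.74 (adjuvant recommended) with 1.35 (surgery alone recommended).

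**4. Whether the remedy removes it.** Starting the clock at the end of the delay, in patients still event-free, gives about 1.00 when all are recommended adjuvant therapy and half are planned for it, at delays of 1, 2 and 3 months. That handles timing but not differences in risk between recommended regimens. Assume half are recommended adjuvant therapy, hazards of 0.8 and 0.25 per year in the two recommendation groups (overall 12-month RFS about 61%), adjuvant therapy planned in 70% and 50% of them, and a 2-month delay. The landmark alone then gives 1.26. Landmark plus stratification by recommended regimen gives 1.00.

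**The case against.** The strongest reply is that the bias belongs to an analysis the protocol does not describe. A reader might infer that a surgery start would favour the consistent group by about the planned effect, and so could produce HR 0.7 by itself. The documents do not support that:

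- No section starts RFS at surgery. Patients are enrolled postoperatively, so enrolment or the prediction date is at least as natural an origin.
- Section 3.1 groups by clinical decision, not by treatment delivered. If the decision is fixed at or before time zero, no immortal time arises.
- Surgery alone is one of the four regimens, so the direction depends on a recommendation mix that is not given. In the table, values near or below 0.7 occur only at the top of the recommendation range with longer delays or more patients planned for therapy.

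A reader might also infer that the model sends low-risk patients to surgery alone, or that this cohort exists to justify the RCT. The protocol says neither. Nor is adjustment limited to age, gender and TNM stage: section 3.8 offers those as examples, and section 3.5 adds vascular invasion and AFP.

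All of this stands against a claim of known size and direction. It does not supply the missing time origin or the missing decision date. Nor is this a detail left to a statistical analysis plan, because the protocol states a definition and that definition does not fit this cohort.

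**Conclusion.** The point holds in limited form. It is certain from the text that RFS and OS, as defined, cannot be computed for the 1,000 observational patients, although RFS is their primary endpoint. It is also certain that the consistency grouping has no date. The RCT definition is sound.

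Immortal-time bias is a possibility of unknown size and direction. The span of 0.53 to 1.89 under no effect, against a planned 0.7, shows that the choice of origin can matter as much as the effect sought. It does not predict what the study would find. It rests on the assumed delay, the share planned, the recommendation mix, constant hazards, a surgery start and grouping by delivered treatment. The definition should be corrected before the cohort's data can influence the choice.

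**What to change.** For the observational cohort:

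- Start RFS and OS on the date when both the model prediction and the clinical decision are recorded, or at one fixed landmark.
- Include in this comparison only patients alive and recurrence-free on that date.
- Fix the consistent or inconsistent label on that date, whatever is later delivered.
- Stratify the Cox comparison by model-recommended regimen, and adjust for the factors already named in sections 3.5 and 3.8: TNM stage, vascular invasion, AFP, age and gender. Stratifying by centre as well is not needed: four regimens by 10 to 15 centres would give up to 40 to 60 sparse strata.

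Keep randomisation as the origin for the RCT only.

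The cost is protocol wording and one date field. Patients with events before the new origin leave the comparison. If patients were followed from surgery and the gap were 3 months, the plan's own hazards would remove about 500 × (1 − e^(−0.511 × 0.25)) + 500 × (1 − e^(−0.511 × 0.7 × 0.25)) = 60 + 43 = 103 of the 471 expected events. That leaves about 368 before dropout, still above 256. Stratification costs some further precision.
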